Description of Study Intervention:	Participants will be randomized 1:1 to active intervention vs. standard of care using a stratified permuted block design by anemia type (iron-responsive vs. inflammatory) and ICU admission indication (surgical vs. non-surgical).
	
The intervention arm is multi-faceted with 3 primary components:
 
1) Optimized phlebotomy, defined by:
 

• minimal volume draws

• closed-loop blood sampling

• bundling of similarly timed labs, all performed by a dedicated phlebotomy team independent from the treatment team

 
2) Decision support aids, including:
 

• visual and electronic alerts reminding the care team to minimize non-essential laboratory testing, mitigate patient-specific bleeding risk

• daily communication with the ICU care team during clinical rounds to reiterate the purpose of the study

 
3) Pharmacologic anemia treatment (given immediately following randomization) targeted to 2 broad groups:
 

1) Anemia responsive to iron supplementation (i.e. 1000 mg IV low molecular weight iron dextran), and

2) Anemia of inflammation requiring erythropoietic stimulation (i.e. 40,000 units of subcutaneous erythropoietin +/- iron supplementation as needed to augment iron stores prior to EPO dosing)

Study Duration:	2 years
Participant Duration:	3 months post-hospitalization, EMR review by study staff at 12 months post-hospitalization

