To assess the impact of the intervention on RBC transfusions	Allogeneic RBC transfusions (units) [Time frame: hospitalization, through 3-months post-hospitalization]	Anemia management may directly result in reductions in RBC transfusions
To assess the impact of the intervention on unplanned hospital readmissions through 12-months post-hospitalization.	Unplanned hospital readmissions [Time frame: 12 months]	Previous data suggests that anemia treatment with iron therapies may reduce hospital readmissions
To assess the impact of the intervention on mortality through 12-months post-hospitalization	All-cause mortality [Time frame: 12 months]	Previous data suggests that IRON and EPO may reduce mortality during and after critical illness

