#### 4.4 END OF STUDY DEFINITION

A participant is considered to have completed the study if they have completed all phases of the study including the last visit shown in the Schedule of Activities (SoA), Section 1.3. Data on mortality and hospital readmission will be extracted at 12-months post-hospitalization for each patient by review of the electronic medical record.

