### 5 STUDY POPULATION

#### 5.1 INCLUSION CRITERIA

To be eligible to participate in this study, an individual must meet all the following criteria:

1. Provision of signed and dated informed consent form (may be completed by legal proxies for those patients unable to provide consent, i.e. sedation/intubation)
2. Stated willingness to comply with all study procedures and availability for the duration of the study, including follow-up assessments
3. Male or female, age  $\geq$  18 years
4. Current ICU admission at Mayo Clinic Rochester
5. Current ICU duration  $\leq$  7 days
6. Patients embedded in the local or regional Mayo Clinic Health System to facilitate post-hospitalization outcome assessment
7. Moderate-to-severe anemia (i.e. hemoglobin concentration  $< 10$  g/dL) at the time of enrollment, with the hemoglobin concentration assessed no more than 24 hours prior to enrollment. If RBC transfusion has been administered between the qualifying hemoglobin assessment and enrollment, a repeat hemoglobin will be required prior to enrollment to ensure that it remains  $< 10$  g/dL.

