Analyses will use Wilcoxon rank-sum tests to compare the distribution of each outcome between groups at each timepoint since assumptions including normality of residuals are not expected to be satisfied for these outcomes. Additional, when applicable, a cutpoint defining a clinically actionable adverse outcome may be defined, for example, defining depression by HADS-Depression  $\geq 8$ . Binary outcomes will be summarized as proportion and compared by randomized arm using a Chi-square test. Death and dropout will be assumed MAR in the primary approach and multiple imputation will be used to impute missing values. Analyses will be conducted on each imputed dataset and results combined to reflect uncertainty due to missing data. An additional analysis will consider a worst-value imputation for mortality, assigning death the worst possible outcome.

Mortality and readmission through 1 year post-discharge will be described by randomized arm using cumulative incidence estimates, censoring subjects at last known contact with the Mayo medical system when status is unknown at 1 year. Inferential analyses will use log-rank tests and Gray's test for mortality and readmission outcomes, respectively.

Since the goal is to provide robust data for further clinical trial evaluation, secondary and exploratory outcomes will be assessed without adjustment for multiplicity, with conclusions from each based on a two-sided alpha level 0.05 statistical test.

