#### 9.4.9 EXPLORATORY ANALYSES

Multiple exploratory analyses have been planned as outlined throughout the protocol. These will be utilized to inform a definitive multicenter phase III clinical trial.

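### Censoring at last Mayo contact, with the chart read at 12 months and no lag, ties follow-up to outcome, so 1-year mortality and readmission can be overstated

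*Combined protocol and SAP*

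**What the plan says.** Section 9.4.3 sets the estimator: "Mortality and readmission through 1 year post-discharge will be described by randomized arm using cumulative incidence estimates". Its censoring rule is "censoring subjects at last known contact with the Mayo medical system when status is unknown at 1 year". It then adds: "Inferential analyses will use log-rank tests and Gray's test for mortality and readmission outcomes, respectively". Each test is two-sided at 0.05 with no multiplicity adjustment.

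The data source is in section 4.4: "Data on mortality and hospital readmission will be extracted at 12-months post-hospitalization for each patient by review of the electronic medical record". The synopsis gives participant duration as "3 months post-hospitalization, EMR review by study staff at 12 months post-hospitalization". The schedule of activities allows ±7 days at 1 month and ±14 days at 3 months, but gives no window or lag for the 12-month review. All-cause mortality status appears only in that 12-month column. The documents describe no 12-month participant contact, name no death registry, and do not define what counts as a contact.

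Section 9.2 calls mortality and readmission unpowered and hypothesis-generating. Section 9.4.9 says of the exploratory analyses in general: "These will be utilized to inform a definitive multicenter phase III clinical trial".

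**The concern.** Kaplan-Meier and cumulative-incidence estimates, and the log-rank and Gray's tests, require that the time at which a patient leaves observation carries no information about the event. Here it can. A charted death or readmission settles a patient's status, so the censoring clause no longer applies and the event counts on its own date. Without an event, the patient stays at risk for the full year only if some contact shows 12-month status. If the chart is read on day 365, almost nobody can have a contact on or after that day. Event-free time after the last contact is dropped, while events in the same stretch are kept.

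At stake are the 12-month mortality and readmission rates. These are listed secondary endpoints, are compared again in the safety section, and are natural inputs for sizing a later trial.

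**Working it through.** **1. Plan figures.** The documents state no expected 1-year mortality or readmission rate and no contact frequency, so there is no figure to reproduce. The 100 patients are randomized 1:1, or 50 per arm. Every rate and gap below is an assumption.

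**2. Two patients under the rule.** Both were last seen in month 10. One is alive at 12 months with no later contact: status is unknown, and censoring is at month 10. The other dies in month 11 and the death is charted: status is known, and the event counts at month 11. The outcome alone decides whether month 10 to 11 is observed.

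**3. Hand calculation at month 11.** Assume 100 patients and 20 deaths spread evenly over the year, all charted, so 20/12 = 1.67 deaths per month. Let the chart be read at month R, and let the gap back from the read to a survivor's last contact be exponential with mean g months. Then

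number at risk at month t = deaths still to come + 80 × [1 − exp(−(R − t)/g)].

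Deaths still to come at month 11 are 1.67. With g = 2:

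- Truth: 1.67 / (80 + 1.67) = 2.0% per month.
- R = 12: 80 × (1 − e^−0.5) = 31.5, plus 1.67 gives 33.1 at risk. The rate is 1.67 / 33.1 = 5.0% per month, about 2.5 times the truth.
- R = 15: 80 × (1 − e^−2) = 69.2, plus 1.67 gives 70.8 at risk. The rate is 1.67 / 70.8 = 2.4% per month.

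**4. Survivors left unconfirmed.** With a lag of L months after month 12, the share is exp(−L/g). For g = 1, 2, 3:

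- L = 0: 100% in each case.
- L = 1: 37%, 61%, 72%.
- L = 3: 5%, 22%, 37%.

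**5. Full-year estimate by simulation.** Settings: 100 patients, 1,500 repeats, true mortality 20%, all deaths charted, random contacts plus the 1- and 3-month visits. Mean Kaplan-Meier mortality at 12 months:

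| Chart read | gap 1 month | gap 2 months | gap 3 months |
|---|---|---|---|
| 12 months | 27% | 32% | 38% |
| 13 months | 20.7% | 22.6% | 24.9% |
| 15 months | 20.1% | 20.8% | 21.9% |

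For the 12-month read, a separate simulation with 45 patients per arm gave 26-36% under a constant hazard and 24-31% under a falling one. Across all runs the day-365 range is about 24-39%.

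For an assumed true readmission of 40%, all within Mayo, the Aalen-Johansen estimate is 48-57% (12-month read), 41-46% (13 months) and 40-42% (15 months).

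**6. If many survivors are confirmed anyway.** With 50% confirmed at 12 months the overstatement is about 1-4 points. With 80% confirmed it is 1.5 points or less.

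**7. If some events never reach the chart.** The ranges cover gaps of 1-3 months.

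| Assumed truth and capture | 12-month read | 13-month read |
|---|---|---|
| Mortality 20%, 75% of deaths charted | 20.6-30.0% | 16.0-19.6% |
| Mortality 20%, 50% of deaths charted | 14.4-22.7% | 10.9-13.5% |
| Readmission 40%, 70% at Mayo | 34-42% | 29-33% |

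**8. Arm comparison.** With equal gaps, the nominal 5% log-rank test rejects a true null 4.9-5.0% of the time. With gaps of 1 vs 3 or 2 vs 4 months it rejects 6.3-7.4% of the time.

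**The case against.** The strongest reply is that the clause is narrow and the setting favourable. It applies only to patients whose 1-year status is unknown, so anyone known to be alive keeps the full year. Enrolment requires "Patients embedded in the local or regional Mayo Clinic Health System to facilitate post-hospitalization outcome assessment", and section 5.5 expects post-hospital care mainly within that system. Contact may therefore be frequent. Nothing forbids a chart pull some weeks after month 12, and one month of lag already brings 27-38% down to 20.7-24.9%. The outcomes are unpowered: for a 20% rate in 50 patients the 95% half-width is 1.96 × √(0.2 × 0.8 / 50) = 11 points, so a bias of a few points would hardly show.

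Much of this stands. A reader might infer that all survivors are censored at their last contact, or that the rates are certainly overstated. The documents support neither. The text limits the rule to unknown status, and unrecorded deaths or admissions elsewhere can outweigh the upward bias, above all for readmission.

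A reader might also infer an inflated type I error. That needs contact gaps that differ between arms. The trial is open-label, so a difference is possible, but both arms share the same follow-up schedule and nothing in the documents points to one.

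What does not stand is leaving the rule as it is. Frequent contact does not help if the chart is read on day 365, because a visit in month 11 still does not show status at month 12. The plan states the read time and gives no lag. Nor is an upward error of unknown size made safe by a downward error of unknown size.

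**Conclusion.** The point holds in conditional form. As written, the censoring rule and the 12-month chart read make observation time depend on outcome, and 12-month mortality and readmission can be overstated. For a true mortality of 20% and full capture, the overstatement is about 4-19 points with a day-365 read (24-39%), at most about 5 points at 13 months, and at most about 2 points at 15 months. This rests on an assumed event rate, mean contact gaps of 1-3 months and every death reaching the chart. It shrinks to 1.5 points or less if 80% of survivors are confirmed, and the net direction can reverse when events are missed. The documents settle none of these quantities.

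Absolute rates are affected first, and the arm comparison only if contact or capture differs by arm. The 1-month hemoglobin analysis is untouched. This is a cheap improvement to unpowered secondary outcomes, and it does not threaten the trial's main conclusion.

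**What to change.** In section 4.4, the schedule of activities and section 9.4.3 (and the participant-duration line of the synopsis):

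1. Extract EMR status at a fixed lag after 12 months, for example 15 months post-hospitalization, for every patient in both arms.
2. Count deaths and readmissions only to day 365, and treat any contact on or after day 365 as confirming 12-month status.
3. Keep last-contact censoring for patients who are still unconfirmed.
4. Add a sensitivity analysis that censors patients with no recorded event at day 365.

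Step 4 should not become the main analysis, because it understates when capture is incomplete. A true mortality of 20% reads as 10% if half of deaths are charted, and a true readmission of 40% reads as 28% if 70% occur at Mayo. It is also worth stating which records identify deaths and outside admissions, since a later read does not recover events that never reach the chart.

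The cost is a short amendment and a later chart pull, with final 12-month results arriving a few months later. No participant visit changes.

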#### 9.4.4 SAFETY ANALYSES

All AEs and SAEs will be presented and compared between groups. Mortality and hospital readmission rates will also be presented and compared between groups.

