**EPO** (i.e. Epoetin alpha), the erythropoiesis stimulating agent utilized in this trial, will be administered as a single 40,000 unit subcutaneous injection after iron supplementation, though iron supplementation will be withheld for those with ferritin > 1000 ng/ml. It has been used in previous clinical trials of anemia management in critical illness, and it is utilized in our current clinical practice for critically ill anemic and post-surgical patients with contraindications to transfusion therapies (i.e. Jehovah’s witness patients). There are short-term risks associated with this therapy, including minor non-allergic adverse reactions (nausea, dizziness, high blood pressure, pruritis; estimated <10%) and major rare adverse reactions (e.g. deep venous thrombosis, uncontrolled hypertension, myocardial infarction; estimated <1%). There is a black box warning for myocardial infarction, stroke, venous thromboembolism, vascular access thrombosis, and mortality when targeting hemoglobin levels >11 g/dL, data which is derived from repeated use of EPO to achieve near-normal hemoglobin levels for patients with chronic kidney disease. In a recent systematic review and meta-analysis of 21 trials in critical illness, the relative risk (RR) for mortality with EPO was 0.82 (95% CI 0.71-0.94). There were no significant differences in serious adverse events (RR 1.11, 95% CI 0.94-1.31) or VTE (RR 1.17, 95% CI 0.87-1.58), though these data do not exclude the potential for a clinically significant increase in the risk for adverse events with EPO therapy. As a longer-term risk, EPO may theoretically increase the risk of tumor progression or recurrence in patients with cancer. However, these concerns are derived from trials in non-surgical oncologic patients utilizing large doses of ESAs for extended periods of time, particularly when targeting normal hemoglobin levels. However, the

overwhelming evidence suggests that EPO use has no significant impact on cancer progression or other adverse oncologic outcomes, particularly when used in low-doses and when pre-treatment hemoglobin concentrations do not exceed 12 g/dL. To this end, EPO is used extensively for preoperative anemia management in patients undergoing oncologic surgery. Additionally, EPO is now recommended for the treatment of anemia in critical ill adults by the French Society of Anesthesia & Intensive Care Medicine (SFAR).

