either IV iron, EPO, or both. Targeted pharmacologic anemia therapies are being employed given that anemia in acute blood loss/post-surgery and true iron deficiency is iron-restricted and responds to iron supplementation alone; hence, the potential harms of EPO (e.g. thrombosis) likely outweigh benefits.

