## 5.2 EXCLUSION CRITERIA

An individual who meets any of the following criteria will be excluded from participation in this study:

1. IV iron or any ESA use (i.e. darbepoetin, Aranesp, erythropoietin, Epojen, Procrit, Retacrit) within 30 days of enrollment. Oral iron is permitted (e.g. oral iron supplements, multivitamin with iron)
2. Severe anemia prior to hospitalization (i.e. hemoglobin consistently  $< 9$  g/dL in the 90 days prior to admission). If hemoglobin is not available or if hemoglobin is  $\geq 9$  g/dL at any time within 90 days prior to enrollment, then this criterion is not met, and the patient may be enrolled
3. Known allergic reactions to IV iron or any EPO agent
4. Inability to complete outcome assessments (i.e. not expected to survive hospitalization, unable to make follow-up appointments, non-ambulatory status preceding hospitalization, dementia or other severe cognitive impairment, visual impairment i.e. blind or legally blind, non-English speaking)
5. Pregnancy or breastfeeding at time of enrollment given unclear safety of EPO
6. Inability to receive pharmacologic venous thromboembolic prophylaxis except in patients with acute blood loss anemia (i.e. recent surgery or gastrointestinal bleeding, extracranial bleeding)
7. Active or suspected thrombosis (i.e. DVT, pulmonary embolism, acute arterial thrombus) within 3 months except in patients with acute blood loss anemia (i.e. recent surgery, gastrointestinal bleeding, extracranial bleeding)
8. Uncontrolled sepsis (i.e. lack of definitive source control and/or  $< 48$  hours of appropriate antimicrobial therapy)
9. Having received  $\geq 10$  units of allogeneic RBCs in the 48 hours before enrollment
10. Acute coronary syndrome (STEMI or NSTEMI) or ischemic stroke within 3 months except in patients with acute blood loss anemia (i.e. recent surgery, gastrointestinal bleeding, extracranial bleeding)
11. Weight less than 40 kg
12. Concerns with study enrollment expressed by the clinical team

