## 6 STUDY INTERVENTION

### 6.1 STUDY INTERVENTION(S) ADMINISTRATION

#### 6.1.1 STUDY INTERVENTION DESCRIPTION

The intervention arm is multi-faceted with 3 primary components:

- 1) **Optimized phlebotomy**, defined by minimal volume draws (i.e. 0.1-2 ml vs. standard 3-10 ml per laboratory order) and closed-loop blood sampling, all performed by a dedicated phlebotomy team independent from the treatment team. This intervention simply requires communication with the phlebotomy team rather than any direct change to patient care.
- 2) **Decision support**. This includes:
  - a. A visual clinical support tool (appendix) urging the clinical team to minimize laboratory assessments and optimize patient bleeding risk. This will be available by the clinical workstations for the ICU team and at the patient's bedside.
  - b. A daily rounding checklist (appendix) accompanied by brief daily discussion (2-minutes) between trained study coordinators and the ICU care team during clinical rounds to reiterate the purpose of the study. The checklist will be available at the clinical workstations for the ICU team.
  - c. Epic direct messages sent twice per day (targeting day and night providers) with the information from the visual support tool to reiterate the purpose of the study.
- 3) **Pharmacologic anemia treatment**. These therapies will be given immediately following enrollment and targeted to 2 broad groups:
  - a. Anemias responsive to iron supplementation alone. This includes patients with anemia secondary to acute blood loss  $\geq$  500 ml and patients with iron deficiency anemia (i.e. ferritin  $<100$  ng/ml or transferrin saturation  $<20\%$ ).
    - Patients with iron-responsive anemias will receive a single total dose infusion (1000 mg) of intravenous (IV) low molecular weight iron dextran (INFeD)
    - This medication is diluted in 500 ml of 0.9% saline. A 25 mg test dose (12.5 ml) is administered over 5 minutes to ensure no immediate hypersensitivity reaction, followed by the completion of the infusion over 1-2 hours (not to exceed 1000 mg/hr). This medication will be given in accordance with Mayo Clinic administration guidelines.

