### 6.3 MEASURES TO MINIMIZE BIAS: RANDOMIZATION AND BLINDING

Participants will be randomized 1:1 to active intervention vs. standard of care using a stratified permuted block design by anemia etiology (iron responsive vs. not) and ICU admission indication (surgical vs. non-surgical). Randomization will occur electronically using the REDCap randomization module. Randomization lists will be developed by the study statisticians and uploaded directly to REDCap. Study staff involved in patient care are unable to access randomization lists in advance and therefore are unlikely to predict future randomization/assignment. Clinicians and subjects will not be blinded to study interventions. However, all data analysts will be blinded to treatment allocation while the study is ongoing.

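### Section 9.4.4 compares adverse events only between whole arms, so a thrombotic excess from EPO, which only one randomization stratum receives, is scaled down by that stratum's share; a descriptive by-stratum table would show it

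*Combined protocol and SAP*

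**What the plan says.** Section 9.4.4 is the whole safety analysis: "All AEs and SAEs will be presented and compared between groups", with mortality and readmission rates treated likewise. It gives no method and no split by stratum or by drug received. Section 9.4.7 plans interaction analyses, one of them by anemia etiology, but only for the primary hemoglobin endpoint.

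Treatment in the active arm differs by stratum. Under section 6.1.1, "Patients with iron-responsive anemias will receive a single total dose infusion (1000 mg) of intravenous (IV) low molecular weight iron dextran (INFeD"), and they get no EPO. The remaining patients receive a single EPO dose, preceded by IV iron when ferritin is below 1000 ng/ml. Section 4.1 explains the split: anemia from blood loss or true iron deficiency is "iron-restricted and responds to iron supplementation alone; hence, the potential harms of EPO (e.g. thrombosis) likely outweigh benefits". Section 6.3 randomizes 1:1 using a "stratified permuted block design by anemia etiology (iron responsive vs. not"), and sections 4.1 and 6.1.1 have etiology adjudicated before randomization.

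Section 2.3.1 lists thrombosis, myocardial infarction and uncontrolled hypertension as EPO risks. It cites a VTE relative risk of 1.17 (95% CI 0.87 to 1.58) from a meta-analysis in critical illness, "though these data do not exclude the potential for a clinically significant increase in the risk for adverse events with EPO therapy".

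Three exclusions in section 5.2 carry a waiver. Criterion 6 reads "Inability to receive pharmacologic venous thromboembolic prophylaxis except in patients with acute blood loss anemia". Criterion 7 (thrombosis within 3 months) and criterion 10 (acute coronary syndrome or ischemic stroke within 3 months) have the same exception.

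**The concern.** The protocol withholds EPO from one stratum because it judges that the balance of harm and benefit differs there. The safety analysis then merges the two strata. Patients who could not have received EPO in either arm contribute their events to the same totals as those who could, and this pulls any EPO-linked contrast toward no difference.

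The section 5.2 waivers may add to this. They admit patients with recent thrombosis, coronary events or stroke, or without VTE prophylaxis, only when the anemia is from acute blood loss. Section 6.1.1 places such patients mainly in the iron-alone stratum, where they would add thrombotic events unrelated to EPO in both arms.

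At stake is how the pilot's harm data are read when the definitive trial is designed. A pooled ratio near 1 could be taken as reassurance about EPO although an unknown part of each arm was never eligible for it.

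**Working it through.** **Plan's own figure.** Section 9.4.4 states none. The sample size in section 9.2, which fixes how many patients the safety tables will hold, reproduces. With SD 1.5 and a difference of 1.0 g/dL, 37 per group gives 80.8% power (noncentral t, two-sided 0.05), against 80% stated. 74/0.75 = 98.7, so 99, against 100 enrolled.

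**Inputs from the documents.** Allocation 1:1 within etiology strata (6.3); EPO only in the not-iron-responsive stratum of the active arm (6.1.1); VTE relative risk 1.17, upper limit 1.58 (2.3.1).

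**Assumptions.** f = share of patients in the EPO stratum; p_E = control-arm event risk in that stratum; p_I = event risk in the iron stratum, the same in both arms (that is, the bundle without EPO does not change thrombosis); k = p_I/p_E.

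**Formulas.**
- Active-arm risk = f·p_E·RR + (1−f)·p_I
- Control-arm risk = f·p_E + (1−f)·p_I
- Pooled risk difference = f·p_E·(RR−1) = f × (EPO-stratum risk difference)
- Pooled RR = 1 + (RR−1)·f/[f + (1−f)·k]

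**Results.** A 10-point excess in the EPO stratum appears as 3, 5 or 7 points at f = 0.3, 0.5 or 0.7. For the relative risk:

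| f | True 1.58, k = 1 | True 1.58, k = 2 | True 1.17, k = 1 |
|---|---|---|---|
| 0.20 | 1.12 | 1.06 | 1.03 |
| 0.35 | 1.20 | 1.12 | 1.06 |
| 0.50 | 1.29 | 1.19 | 1.09 |
| 0.70 | 1.41 | 1.31 | 1.12 |

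Example: f = 0.50, k = 1 gives 1 + 0.58 × 0.50 = 1.29; with k = 2 it gives 1 + 0.58 × 0.50/1.50 = 1.19.

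**How plausible is k = 2?** Only the waived patients raise the iron stratum's background risk. If they made up 20% of it, their risk relative to the others, x, would have to satisfy 0.8 + 0.2x = 2, so x = 6. The k = 2 column illustrates direction and is not an estimate.

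**Precision** (Fisher's exact test, two-sided 0.05, 50 per arm, true stratum RR of 3). At f = 0.5, the stratum comparison (25 v 25) has 7% power if p_E = 5% and 31% if p_E = 10%. The pooled comparison has about 6% and 17–21%, depending on p_I. Over f = 0.3 to 0.7, p_E = 5 or 10% and p_I = 5 to 20%, power is 3–46% by stratum and 3–38% pooled. Zero events among n EPO-treated patients leaves a one-sided 95% upper bound of 1 − 0.05^(1/n): 18% for n = 15, 11% for n = 25, 8% for n = 35.

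**The case against.** The strongest reply is that the trial tests a bundle against usual care, so the arm comparison in 9.4.4 is the harm comparison that matches the design. Section 3 lists no EPO safety objective, and the statement in 2.3.1 is background on risk. This stands. A reader might infer that the plan fails to answer a safety question it has set itself; the documents do not support that. The pooled comparison is valid for the bundle, and what it lacks is a view of the stratum that carries the EPO risk.

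Other parts of the reply also stand:

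- **The within-stratum contrast does not isolate EPO.** Active patients there also receive IV iron when ferritin is below 1000 ng/ml, low-volume phlebotomy, and prompts for early removal of arterial and central lines (Appendix 1). The contrast is the bundle including EPO against usual care.
- **Two of the six listed event types cannot be compared between arms.** Section 8.3.1 ties infusion reactions and hypertensive events to study drug administration. Controls receive neither drug nor placebo (4.2), so they cannot have these events as defined.
- **The loss is not always large.** A reader of the rows with smaller shares might conclude that at least half of the excess always disappears. With equal background risk and f = 0.70, 30% is lost (46% with k = 2).
- **Neither analysis has useful power**, and at f = 0.20 the EPO stratum would be about 10 v 10 patients (50 × 0.20). That argues against a formal test by stratum, not against showing the counts.

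It can also be said that 9.4.4 does not forbid stratum tables, that 8.3.3.2 requires a causality grade for each event, and that the Data and Safety Monitoring Plan (10.1.6), which is not among the documents, may look by stratum. None of these puts the breakdown into the planned final analysis.

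**Conclusion.** The point holds as a gap in harm reporting that should be closed. It does not affect the primary endpoint. Whenever some patients fall in the iron-responsive stratum, the pooled risk difference is the EPO-stratum difference multiplied by f, provided the rest of the bundle has no effect on thrombosis. At the cited upper limit of 1.58 and equal background risk, the pooled ratio lies between about 1.12 and 1.41 for shares of 20 to 70%. At the cited point estimate of 1.17 it lies between 1.03 and 1.12. The documents give neither the share nor the background risks, so these are ranges and not predictions.

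The waivers would lower the pooled ratio further if they raise background risk in the iron stratum, but by how much cannot be said. Their match to that stratum is also not assured: 5.2 gives no blood-loss volume, 6.1.1 requires at least 500 ml, and the exclusion table in 2.3.3 shows no waivers. The basic dilution does not depend on the waivers.

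**What to change.** In section 9.4.4:

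1. Keep the pooled comparison as the bundle-level summary.
2. Add a descriptive table of VTE, myocardial infarction, non-hemorrhagic stroke, bloodstream infection, SAEs and deaths by arm within anemia-etiology stratum (four columns), with counts and exact 95% intervals. State that the not-iron-responsive contrast is the bundle including EPO against usual care.
3. Report infusion reactions and one-hour hypertensive events only as counts among treated patients, by drug received (iron alone, EPO alone, both).
4. State that the table is descriptive and that no stratum-level test will be used to conclude safety.

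Separately, reconcile the section 5.2 waivers with the table in 2.3.3 and with the blood-loss threshold in 6.1.1, so that it is clear which stratum waived patients enter.

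The cost is a few table columns. Etiology is recorded and randomized on, the events are already collected, and the within-stratum comparison keeps the protection of randomization. The drawback is small cells and wide intervals.
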